#### **4.7 HANDLING OF SUBJECT WITHDRAWAL**

In case of withdrawal of consent and unless otherwise stated by the subject in the withdrawal of consent, PI(s) will be encouraged to obtain information from the subject in order to follow the medical status of the subjects (especially when the subject withdraws his/her consent after having experienced an AE/SAE or an efficacy endpoint). Principal investigator or designee(s) must make reasonable attempts to contact subjects that are lost to follow-up, in order to obtain health status and reason for withdrawal. These attempts must be documented in the medical records.

	Approved by: [name] [name]	Protocol No.: SARO.17.004.02.PROTOCOL Version No.: 2.0
--	---	---

### 5.1.2 Comparator Drug Description

Placebo will be used as comparator, which will be formulated as tablets, and will contain above mentioned excipients without Saroglitazar Magnesium [REDACTED] [REDACTED] [REDACTED]. The IP will be manufactured following current-Good Manufacturing Practice (cGMP) guideline.

### 5.2 DOSAGE AND TREATMENT SCHEDULE

Subjects will receive either Saroglitazar Magnesium 2 mg or 4 mg or placebo orally once each morning before breakfast for a period of 24-week.

However, on the day of the scheduled clinical visit, subjects will have the IP administered on site after fasting blood sample collection. If on the day of a scheduled clinic visit the subject has already taken the IP, all procedures except blood sample collections will be performed. The subject will be asked to return the next day to have the blood sample collected, and will be reminded not to take the IP until after the blood sample collections. If the subject again returns

having taken the IP, blood samples will be collected and the subject will be asked to return for the next scheduled visit.

### 5.3 PACKAGING, LABELLING AND SUPPLY

Study drugs will be packed, labelled and supplied by the Sponsor according to all local regulatory requirements. [REDACTED]

[REDACTED]

[REDACTED]. The PI or designee will confirm the receipt of IP in writing via fax/email.

[REDACTED]

Unused drug supplies will be returned to the Sponsor (or designee) for destruction/ destroyed at the site after approval for the same by the Sponsor. No study drug will be destroyed or returned until complete drug accountability has been performed by the study monitor. All supplies must be accounted for at the end of the study period.

At the time of or in proximity to the site initiation, each Investigator will be provided sufficient supply of study drug. Investigational product must be dispensed to each subject in such a way that the subject can take the doses in accordance with the Protocol. A drug accountability log(s) for recording the receipt, dispensing and return of the IP must be maintained by the PI or any designated personnel. The drug accountability log(s) must be kept up to date and must be made availability to the study monitor during monitoring visits.

A temperature log must be maintained that the drug supplies are stored at the correct temperature throughout the study period.

### 5.4 STORAGE CONDITIONS

Investigational products will be stored at room temperature (20°C to 25°C or 68°F to 77°F) in a dry place away from light at the study site or pharmacy. If the IP temperature extends outside the

 Zydus Discovery DMCC	CLINICAL TRIAL PROTOCOL Saroglitazar Magnesium – Phase 2 SARO.17.004	CONFIDENTIAL Page 37 of 76
--	---	---

20-25°C range, a temperature excursion must be documented in the study-specific temperature log, and sent to the Sponsor. If the excursion is within 15-30°C, quarantine is not required, and the IP is acceptable for use. If the excursion is outside of the 15-30°C range, the IP must be quarantined until a decision on the stability of the IP is made by the Sponsor. If the excursion goes beyond the range of 15-30°C it will be considered as a protocol deviation. Protect the IP from light. All IP supplies in the study will be stored in a secure location with access limited to the Site Pharmacist or the PI designated site staff.

### **5.5 BLINDING/UNBLINDING**

The study will be performed in a double-blind manner. All study drug will be supplied in identical packages and study drug kits. The study drug tablets will be similar in color, smell, taste and appearance, thereby maintaining double-blind conditions.

The blinding should not be broken except in a medical emergency where knowledge of the study drug received would affect the treatment of the emergency.

The blinding must only be broken following a discussion on a case-by-case basis, at the discretion of the Sponsor/Medical Expert. If an emergency unblinding becomes necessary, the PI should notify the Sponsor/Medical Expert, if possible, before unblinding. If it is determined that unblinding is necessary, a scratch card/blinding envelop will be decoded to reveal the treatment received by the patient. All cases resulting in an unblinding event will be documented and reported to the Medical Expert and the Sponsor. If the blind is broken, the date, time and reason must be recorded in the patient's eCRF/source document and any associated AE report completed.

The overall randomization code will be broken only for reporting purposes. This will occur once all final clinical data have been entered into the database, all data queries have been resolved, and the assignment of patients to the analysis sets has been completed.

### **5.6 METHOD OF ASSIGNING SUBJECT TO TREATMENT GROUP**

Patients will be randomly assigned in a 2:2:1 ratio to Saroglitazar Magnesium 2 mg or 4 mg or placebo. The block randomization schedule will be generated using SAS® software (Version: 9.4 or higher; SAS Institute Inc., USA)..

	Approved by: [name] [name]	Protocol No.: SARO.17.004.02.PROTOCOL Version No.: 2.0
--	------------------------------------	---

 Zydus Discovery DMCC	CLINICAL TRIAL PROTOCOL Saroglitazar Magnesium – Phase 2 SARO.17.004	CONFIDENTIAL Page 38 of 76
---	---	---

## 5.7 SELECTION OF DOSES

Saroglitazar Magnesium 1 mg, 2 mg and 4 mg have favorably modified the lipid profile in the dyslipidemic patients during its development in Phase II and III studies. Based on the safety and efficacy results of Saroglitazar Magnesium, it was approved in India at the doses of 2 mg and 4 mg QD for the treatment of “Diabetic Dyslipidemia” and “Hypertriglyceridemia with T2DM not controlled by statin therapy”. Based on these results, Saroglitazar Magnesium 2 mg and 4 mg doses have been selected for this study.

## 5.8 CONCOMITANT MEDICATIONS AND OTHER RESTRICTIONS

### 5.8.1 Previous and Concomitant Medications

[figure not shown]
Any medication the subject takes other than the study drug, including herbal and other non-traditional remedies, is considered a concomitant medication. All concomitant medications and any changes in the dosage or regimen of a concomitant medication for the 30 days preceding Visit 1 until the end of the study (i.e., the safety follow-up) must be recorded in the CRF.

### 5.8.2 Restricted Concomitant Medications

Drugs affecting insulin resistance (Glitazones/Glitazars/GLP-1 agonists) will not be allowed during the study.

Other drugs claimed for treatment of NASH (pentoxifyllin, ursodeoxycholic acid, antioxidants such as vitamin E (>800 IU/day), glutathione, orlistat, betaine, incretin mimetics or non-prescribed complementary alternative medications (including dietary supplements, megadose vitamins, herbal preparations and special teas) will not be allowed during the study. *However, patients who are taking stable dose of Vitamin E for at least 3 months will be enrolled in the study.*

Subjects also should not take any non-allowed over-the-counter medications or complementary and/or alternative medications believed to have a potential impact that would affect the ability to evaluate the study data.

	Approved by: [name] [name]	Protocol No.: SARO.17.004.02.PROTOCOL Version No.: 2.0
---	------------------------------------	---

 Zydus Discovery DMCC	CLINICAL TRIAL PROTOCOL Saroglitazar Magnesium – Phase 2 SARO.17.004	CONFIDENTIAL Page 39 of 76
---	---	---

### 5.8.3 Permitted Concomitant Medications

With the exception of excluded concomitant medications, other medications that subjects have been taking at stable dosages for at least 3 months prior to biopsy, i.e., statins, drugs for glycemic control and hypertension will be permitted as concomitant medications. To the extent possible, subjects should continue with their current regimen of medication without any change throughout the study.

[figure not shown]
Allowed over-the-counter medications include acetaminophen (maximum 1 gram/day), ibuprofen (maximum 800 mg/day) or naproxen (maximum 440 mg/day) or antacids such as H2 receptor blockers or proton-pump inhibitors for shorter duration as per Investigator discretion.

The PI should be alerted if, during the course of the study, a subject requires a new medicine or therapy or a change to an established dosing regimen. All medications that target NAFLD or NASH, or have been suggested to target the underlying causes of NAFLD or NASH, should be reviewed and agreed on by the PI, Medical Expert and Sponsor before being taken by the subject.

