## 1 STUDY FLOW CHART

*NOTE: Liver biopsy showing NASH within 6 months preceding Visit 1 can be used.*

 Zydus Discovery DMCC	CLINICAL TRIAL PROTOCOL Saroglitazar Magnesium – Phase 2 SARO.17.004	CONFIDENTIAL Page 20 of 76
---	---	---

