#### 4 STUDY POPULATION

Subjects clinically suspected of NASH and having laboratory evidence of abnormally elevated liver function tests (LFT) suggestive of NASH and confirmed histologically by biopsy will be recruited for the study. The histological evidence of NASH is defined as NAS  $\geq 4$  with a minimum score of 1 for all of its three components [steatosis, hepatocyte ballooning and lobular inflammation].

If the subject has consumed restricted medications but is otherwise considered eligible to be enrolled in this study by the Investigator, then a minimum of 1 month wash out period will be instituted before the screening visit.

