##### 4.2 INCLUSION CRITERIA

1. Patients able to provide written informed consent for participation in this trial.
2. Males or females, 18 to 75 years of age, both inclusive.
3. Female must be either of non-child bearing potential (surgically sterilized at least 6 months prior to screening or postmenopausal) or using one or more methods of contraception.
4. Histologic confirmation of NASH without cirrhosis (fibrosis stage 0, 1, 2, or 3) from liver biopsy performed either during the screening period or no more than 6 months prior to the first visit, with a NAS of  $\geq 4$  and a score of at least 1 in each (steatosis scored 0-3, ballooning scored 0-2 and lobular inflammation scored 0-3). If biopsy was performed within 6 months of screening, the slides, biopsy material or block should be available for baseline documentation. Such patients, whose historical biopsy report is available, should not use medications suspected of having an effect on NASH for at least 3 months prior to the screening.
5. BMI  $\geq 25$  kg/m^2.

	Approved by: [name] [name]	Protocol No.: SARO.17.004.02.PROTOCOL Version No.: 2.0
---	---	---

 Zydus Discovery DMCC	CLINICAL TRIAL PROTOCOL Saroglitazar Magnesium – Phase 2 SARO.17.004	CONFIDENTIAL Page 28 of 76
--	---	---

6. For hypertensive patients, blood pressure must be controlled by a stable dose of antihypertensive medications for at least 3 months prior to screening (and the stable dose can be maintained throughout the study)
7. Patients with type 2 diabetes mellitus may be included if they fulfil the following criteria;
  - a. Stable therapeutic regimen as defined by no changes in oral agents or dose for at least 3 months before screening and the stable dose can be maintained throughout the study.
  - b. HbA1c  $\leq$  9.5%.
8. Patients agree to comply with the study procedure.

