13. Use of drugs that are known CYP2C8 inhibitors/substrate.
14. Use of drugs associated with a clinical or histological picture consistent with fatty liver disease or NASH for more than 12 consecutive weeks in the 1 year prior to start of the study; (these include amiodarone, tamoxifen, methotrexate, glucocorticoids, anabolic steroids, tetracyclines, estrogens, valproate/valproic acid, chloroquine, anti-HIV drugs).
15. History of thyroid disease (hypothyroid patients who are euthyroid on thyroid hormone replacement can be included).
16. History of, or current, cardiac dysrhythmias.
17. History of bariatric surgery, or undergoing evaluation for bariatric surgery.
18. Patients with a >10% weight loss in the 3 months prior to screening.
19. History or other evidence of severe illness or any other conditions that would make the patient, in the opinion of the Investigator, unsuitable for the study (such as poorly

	Approved by: [name] [name]	Protocol No.: SARO.17.004.02.PROTOCOL Version No.: 2.0
---	------------------------------------	---

 Zydus Discovery DMCC	CLINICAL TRIAL PROTOCOL Saroglitazar Magnesium – Phase 2 SARO.17.004	CONFIDENTIAL Page 30 of 76
--	---	---

controlled psychiatric disease, coronary artery disease, HIV or active gastrointestinal conditions that might interfere with drug absorption).

20. Patients on any treatment with other drugs used for treatment of NASH [pentoxifyllin, ursodeoxycholic acid, antioxidants such as vitamin E (>800 IU/day), glutathione, orlistat, betaine, incretin mimetics or non-prescribed complementary alternative medications (including dietary supplements, megadose vitamins, herbal preparations and special teas)] or any medicine in clinical trials for NASH. *(However, patients who are taking stable dose of vitamin E for at least 3 months prior to screening will be enrolled in the study).*
21. History of other causes of chronic liver disease [autoimmune, primary biliary cirrhosis, hepatitis B virus (HBV) and hepatitis C virus (HCV), Wilson disease, alpha-1-antitrypsin deficiency, hemochromatosis etc.

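### For a historical baseline biopsy more than 3 months old, the ban on NASH-active drugs does not reach the biopsy date, and vitamin E could be started after it

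*Protocol*

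**What the plan says.** **Baseline.** Protocol Section 4.2, criterion 4, accepts a biopsy taken during screening or "no more than 6 months prior to the first visit". The note to the Study Flow Chart agrees: "Liver biopsy showing NASH within 6 months preceding Visit 1 can be used". The historical material then supplies the baseline reading. The primary endpoint is the change in NAS from that reading to Week 24, with no worsening of fibrosis (Protocol 6.2.1, SAP 6.2).

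**Drug rules and the date each counts from.**
- Criterion 4, for historical-biopsy patients only: they "should not use medications suspected of having an effect on NASH for at least 3 months prior to the screening". Anchor: screening.
- Exclusion 20: "Patients on any treatment with other drugs used for treatment of NASH". This describes current use. It excepts vitamin E at a stable dose for 3 months before screening. Section 5.8.2 repeats the exception without naming a date to count from.
- Section 4, for restricted drugs: "a minimum of 1 month wash out period will be instituted before the screening visit". Anchor: screening.
- Criterion 7a, for type 2 diabetes: "no changes in oral agents or dose for at least 3 months before screening". Criterion 6 treats antihypertensives in the same way. Anchor: screening.
- Section 5.8.3 permits "other medications that subjects have been taking at stable dosages for at least 3 months prior to biopsy". Anchor: biopsy. It adds that, as far as possible, "subjects should continue with their current regimen of medication without any change throughout the study".

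**Recording.** Section 5.8.1 requires concomitant medications in the CRF from 30 days before Visit 1. Section 7.2 also has prior medication reviewed and recorded at Visit 1. SAP Section 5 summarises prior therapies and lists them with start and stop dates.

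**The concern.** Criterion 4's drug ban was written for patients whose baseline is a historical biopsy, so its evident purpose is to keep drug effects out of the baseline NAS. Counting from screening does not achieve this once the biopsy is more than 3 months old.

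If a drug had lowered NAS at the baseline biopsy and was then stopped, the loss of that effect would fall between baseline and Week 24 and be read as part of the on-study change. In the saroglitazar arms this makes the within-arm change look less favourable than it is. Vitamin E started after the biopsy would work the other way. With arms of 6, 6 and 3 patients (Section 4.1), one such patient has visible weight in a mean.

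**Working it through.** The plan states no figure on this point to reproduce. The check puts the windows on one time axis.

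**Inputs.** Visit 1 is month 0 and the biopsy is at month −B, with B up to 6 (criterion 4). The criterion 4 ban covers months −3 to 0. Planned arm sizes are 6, 6 and 3.

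**Step 1: what criterion 4 covers.** Guaranteed drug-free time before the biopsy is max(0, 3 − B). Time after the biopsy that the ban does not cover is max(0, B − 3). A window running from 3 months before the biopsy through Visit 1 would be B + 3 months long.

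| B (months) | Drug-free time guaranteed before biopsy | Time after biopsy not covered | Length of biopsy-anchored window |
|---|---|---|---|
| 1 | 2 | 0 | 4 |
| 2 | 1 | 0 | 5 |
| 3 | 0 | 0 | 6 |
| 4 | 0 | 1 | 7 |
| 5 | 0 | 2 | 8 |
| 6 | 0 | 3 | 9 |

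Up to B = 3 the ban still reaches the biopsy date. Beyond that it does not.

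**Step 2: does another rule close the gap?** Take a biopsy at month −6 taken on a NASH-active drug that was stopped at month −4.
- Criterion 4: no use in months −3 to 0. Passes.
- Exclusion 20: not on the drug now. Passes.
- Washout in Section 4: at least 1 month before screening. Passes.
- Section 5.8.2: applies during the study. Passes.
- Exclusion 6, if the drug was investigational: 3 months before screening. Passes.

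**Step 3: vitamin E.** Take a biopsy at month −6 and vitamin E started at month −4 at a stable dose. It has been stable for 4 months at screening, so the exception is met, yet the baseline biopsy was taken without it and the Week 24 biopsy would be taken on it. This assumes that the exception also overrides criterion 4, which the protocol does not say.

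**Step 4: possible size.** The documents give no NAS effect for these drugs. Assume d = 0, 0.5 or 1 point in one patient.
- Active-arm mean: d/6 = 0, 0.08 or 0.17.
- Placebo mean: d/3 = 0, 0.17 or 0.33.
- If only that patient is affected, the difference from placebo moves by the same amount.

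**Step 5: balance.** If k of the 15 patients are affected and allocated at random, the probability that placebo has none is C(12,k)/C(15,k).
- k = 1: 12/15 = 80%.
- k = 2: 132/210 = 63%.
- k = 3: 1320/2730 = 48%.

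Randomisation balances the error in expectation, but an even split cannot be relied on at this size. The values of k are illustrative, because the documents do not say how many historical biopsies are expected.

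**The case against.** The strongest reply is that this matters little. Section 2.2 reports that trials of metformin, thiazolidinediones, statins, antioxidants and pentoxifylline reached no positive conclusion. No formal hypothesis testing is planned, and the error from a stopped drug works against saroglitazar within its own arms. The shifts in Step 4 rest on assumed effects. All of this stands and limits the point to a minor one. It does not remove it, since the protocol itself bars these drugs in these patients.

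Four stronger readings are tempting, and the documents do not support them.
- *Any historical biopsy may be taken on a NASH-active drug.* No: for a biopsy up to 3 months old, the biopsy date lies within the ban.
- *Statin and diabetes drug doses are uncontrolled between biopsy and screening.* This needs a narrow reading of Section 5.8.3. Its wording about drugs that patients have been taking at stable doses, and its reference to their current regimen, can fairly be read as stability continuing to the present. The text deserves clarification, but is not shown to be defective.
- *Non-oral glycaemic drugs are a further gap.* GLP-1 agonists and incretin mimetics are already barred, so this is mainly insulin. Freezing insulin doses for up to 9 months would be disproportionate.
- *Such changes would go unseen.* The 30-day CRF window is not the only record. Section 7.2 and SAP Section 5 also cover prior medication, although no look-back is stated.

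The absence of a closing rule is judged on the text available. The schedule of assessments (Table 1) and Sections 5.9 and 5.10 are not in it.

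**Conclusion.** The point holds for historical biopsies more than 3 and up to 6 months before Visit 1. A patient can satisfy every drug rule set out above and still have a baseline NAS read while on a NASH-active drug that was later stopped. On the assumption in Step 3, a patient can also start vitamin E after the baseline biopsy.

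The consequence is an error in that patient's Week 24 NAS change. It stays in the within-arm means and is non-differential between arms in expectation. Its size is not given in the documents and is probably small; the figures in Step 4 show only what an assumed effect of up to 1 point would do.

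A reader might infer that the comparison with placebo is biased. The documents do not support that. Eligibility is settled before randomisation, and SAP 6.4 leaves it unclear whether its treatment differences extend to the primary NAS change, which is in neither of its test lists. This is an inexpensive improvement, not a threat to the study's conclusions.

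**What to change.** For historical-biopsy patients only:
1. In criterion 4 (Section 4.2 and synopsis), and where its wording recurs (synopsis Methodology and Liver biopsy Visit, Sections 7.1 and 7.2), bar any medication suspected of an effect on NASH from 3 months before the qualifying biopsy through Visit 1.
2. Tie the vitamin E exception (exclusion 20 in Section 4.3 and the synopsis, Section 5.8.2, synopsis Restricted Medications) to a stable dose over the same window.
3. As a clarification, state in Section 5.8.3 and the synopsis Concomitant Medication text that statin and oral glycaemic drug doses stay stable over that window, and have the Visit 1 prior-medication review cover it.

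Do not bar insulin dose adjustment. Leave criterion 6 and the on-study stability request as they are, and require no repeat biopsy.

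The cost is protocol wording, slightly narrower eligibility in a 15-patient study, and a medication history of up to 6 + 3 = 9 months for these drugs. Exclusion 14 already needs a 1-year history for the drugs it lists, and applying Section 5.8.3 as written to a 6-month-old biopsy already reaches back 9 months.

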### 5.8.4 Other Restrictions

#### 5.8.4.1 Alcohol

Subjects are encouraged to stop alcohol consumption entirely during the study. They are not permitted to consume >1 unit of alcohol per day (>7 units per week) during the study. Alcohol consumption will be recorded throughout the study period.

	Approved by: [name] [name]	Protocol No.: SARO.17.004.02.PROTOCOL Version No.: 2.0
---	------------------------------------	---

 Zydus Discovery DMCC	CLINICAL TRIAL PROTOCOL Saroglitazar Magnesium – Phase 2 SARO.17.004	CONFIDENTIAL Page 41 of 76
---	---	---

## 6 OBSERVATIONS

### 6.1 CRITERIA FOR SAFETY

#### 6.1.1 Safety Variables

The following safety assessments are conducted to evaluate the safety:

- Frequency and severity of adverse events
- Physical Examination will consist of an evaluation of the head, neck, eyes, ears, nose, throat, chest, heart, lungs, abdomen, skin, extremities and the neurological and musculoskeletal systems.
- Body weight
- Vital Signs
- Clinical laboratory testing (hematology, clinical chemistry, serology and urinalysis).
- 12-lead electrocardiogram (ECG).

[figure not shown]
